5.3.1.3. Ibrutinib/Placebo: Overdose

There is no specific experience in the management of ibrutinib overdose in subjects. No maximum tolerated dose (MTD) was reached in the Phase 1 study in which subjects received up to 12.5 mg/kg/day (1400 mg/day). Healthy subjects were exposed up to single dose of 1680 mg. One healthy subject experienced reversible Grade 4 hepatic enzyme increases (AST and ALT) after a dose of 1680 mg. Subjects who ingested more than the recommended dosage should be closely monitored and given appropriate supportive treatment ([ibrutinib IB](#)).

Refer to Section [11.3](#) for further information regarding special reporting situations as a result of overdose.

5.3.1.4. Ibrutinib/Placebo: Dose Modification for Ibrutinib/Placebo-Related Adverse Reactions

For an ibrutinib/placebo-related adverse reaction, the recommendations for dose modification of ibrutinib/placebo are provided in [Table 4](#) and [Table 5](#) if any of the following hematologic or non-hematologic toxicities occur:

- Grade 3 or greater neutropenia with infection or fever
- Grade 4 neutropenia (ANC<500/ μ L) for more than 7 days. See Section [6.1](#) for instructions regarding the use of growth factor support.
- Grade 3 thrombocytopenia (platelets<50,000/ μ L) in the presence of clinically significant bleeding events.
- Grade 4 thrombocytopenia (platelets<25,000/ μ L).
- Grade 3 or greater non-hematological toxicity (Note: [Table 5](#) recommendations for Grade 3 or higher cardiac failure and cardiac arrhythmias)
- Grade 2 cardiac failure ([Table 5](#))
- Any other Grade 4 or unmanageable Grade 3 hematological toxicity.

If clinically indicated, the use of anticoagulants or antiplatelet agents may be considered for the thromboprophylaxis of atrial fibrillation (Section [6.2.3](#)).

For other grade 3 or 4 AEs, and grade 2 AEs that are deemed per the investigator potentially manageable by dose reduction, these can be managed with a one dose level dose reduction.

In the event that the investigator feels deviation from the recommendations above is required, please consult the Medical Monitor to discuss.

If administration of study drug is delayed or discontinued for toxicity that does not require rituximab to be held for toxicity, rituximab dosing should continue at the investigator's discretion.

Study drug should be discontinued in the event of a toxicity considered to be related to study drug requiring a dose hold lasting more than 28 days, unless reviewed and approved by the Medical Monitor.

Dose changes must be recorded in the Dose Administration eCRF.

Table 4. Ibrutinib/Placebo: Study Drug Dose Modifications for Events not Specified in Table 5

Occurrence	Action to be Taken
First	Withhold study drug until recovery to Grade \leq 1 or baseline; may restart at original dose level (ie, 4 capsules [560 mg/day]) ^a
Second	Withhold study drug until recovery to Grade \leq 1 or baseline; may restart at 1 dose level lower (ie, 3 capsules [420 mg/day])
Third	Withhold study drug until recovery to Grade \leq 1 or baseline; may restart at 1 dose level lower (ie, 2 capsules [280 mg/day])
Fourth	Discontinue study drug

a. When resuming treatment, restart at the same or lower dose based on benefit risk evaluation. If the toxicity reoccurs, reduce daily dose by 140 mg.

For required dose modification for hepatic impairment refer to Section 5.3.1.5 and for concomitant treatment with CYP3A inhibitors refer to Section 6.2.1. If a subject is being dosed at 280 mg due to hepatic impairment or concurrent CYP3A inhibitor administration, dose level is to be reduced by one capsule to 140 mg at the second occurrence of AEs as described above.

Table 5. Ibrutinib Dose Modifications for Cardiac Failure or Cardiac Arrhythmias

Events	Occurrence	Action
Grade 2 cardiac failure	First	Hold study drug until recovery to Grade \leq 1 or baseline; restart at 1 dose level lower (3 capsules [ie, 420 mg daily])
	Second	Hold study drug until recovery to Grade \leq 1 or baseline; restart at 1 dose level lower (2 capsules [ie, 280 mg daily])
	Third	Discontinue study drug
Grade 3 cardiac arrhythmias	First	Hold study drug until recovery to Grade \leq 1 or baseline; restart at 1 dose level lower (3 capsules [ie, 420 mg daily]) ^a
	Second	Discontinue study drug
Grade 3 or 4 cardiac failure Grade 4 cardiac arrhythmias	First	Discontinue study drug

a. Evaluate the benefit risk before resuming treatment.

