5.3.1.2. Ibrutinib/Placebo: Dose and Administration

Study drug (ibrutinib/placebo) is recommended to be self-administered on an outpatient basis. Blinded study medication will be administered for continuous daily dosing.

Study drug (4 capsules) is administered orally once daily. The capsules are to be taken around the same time each day with 8 ounces (approximately 240 mL) of water. The capsules should be swallowed intact and subjects should not attempt to open capsules or dissolve them in water. The use of strong CYP3A inhibitors/inducers, and grapefruit and Seville oranges should be avoided for the duration of the study (Section [6.2.1](#) and [Appendix C](#)).

If a dose is not taken at the scheduled time, it can be taken as soon as possible on the same day with a return to the normal schedule the following day. The subject should not take extra capsules to make up the missed dose.

The first dose will be delivered in the clinic on Cycle 1, Day 1, after which subsequent dosing will be self-administered daily by the subjects typically on an outpatient basis. Please refer to [Table 3](#) and Section [8](#) for oral dose and administration instructions on pharmacokinetic visits; on these days, study drug will be administered in clinic as soon as the subject comes into clinic and after pre-dosing procedures. Pre-medications and rituximab will then be administered as outlined in Section [5.3.2.2](#).

Study drug will be dispensed to subjects in bottles. Unused study drug must be returned to the site and drug accountability records (Section [12.8](#)) updated. Returned capsules must not be redispensed to anyone.

Study drug is continuous (without interruptions) throughout the Treatment Phase. If rituximab infusion is delayed due to scheduling conflicts or toxicity, study drug dosing should continue.

Table 3. Study Drug (Ibrutinib/Placebo) Administration

Study Drug	Ibrutinib/placebo
Schedule of Administration	Daily
Route/Regimen	Oral In-clinic dosing days (Cycle 1, Day 1 and 22; Cycle 3, Day 1): supervised by site staff; given as soon as the subject comes into clinic and after pre-dosing procedures. Pre-medications and rituximab will then be administered. Home administration days: self-administered by subject.
Dose	560 mg (4 x 140 mg capsules) or placebo

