5.3.1.5. Ibrutinib/Placebo: Dose Modification for Hepatic Impaired Subjects

Ibrutinib is metabolized in the liver and therefore subjects with clinically significant hepatic impairment at the time of Screening (Child-Pugh class B or C) are excluded from study participation. For subjects who have at enrollment or develop mild liver impairment while on study (Child-Pugh class A), the recommended dose reduction for ibrutinib/placebo is to a level of 280 mg daily (two capsules). For subjects who develop moderate liver impairment while on study (Child-Pugh class B), the recommended dose reduction is to a level of 140 mg daily (one capsule). Subjects who develop severe hepatic impairment (Child-Pugh class C) must hold study drug until resolved to moderate impairment (Child-Pugh class B) or better. Monitor subjects for signs of toxicity and follow dose modification guidance as needed (refer to [Appendix F](#)).

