6.2. Medications to be Used with Caution

6.2.1. CYP3A Inhibitors/Inducers

Ibrutinib is metabolized primarily by CYP3A4. Concomitant use of ibrutinib and drugs that strongly or moderately inhibit CYP3A can increase ibrutinib exposure and strong CYP3A inhibitors should be avoided.

- Strong inhibitors of CYP3A (e.g., ketoconazole, indinavir, nelfinavir, ritonavir, saquinavir, clarithromycin, telithromycin, itraconazole, nefazodone, and cobicistat) should be avoided and an alternative with less CYP3A inhibitory potential should be considered. If the benefit outweighs the risk and a strong CYP3A inhibitor must be used, see recommended dose modifications in the table below.

- If a moderate CYP3A inhibitor (e.g., fluconazole, erythromycin, amprenavir, aprepitant, atazanavir, ciprofloxacin, crizotinib, diltiazem, fosamprenavir, imatinib, verapamil, amiodarone, dronedarone) is indicated, reduce ibrutinib dose as per recommended dose modifications in the table below. Avoid grapefruit and Seville oranges during ibrutinib/placebo treatment, as these contain moderate inhibitors of CYP3A (see Section 5.3.1.2).
- No dose adjustment is required in combination with mild inhibitors.

Recommended dose modifications are described below:

Patient Population	Co-administered Drug	Recommended Ibrutinib Dose for the Duration of the Inhibitor Use ^a
B-Cell Malignancies	• Mild CYP3A inhibitors	560 mg once daily per indication. No dose adjustment required.
	• Moderate CYP3A inhibitors	280 mg once daily.
	• Voriconazole • Posaconazole at doses less than or equal to suspension 200 mg BID	140 mg once daily.
	• Other strong CYP3A inhibitors • Posaconazole at higher doses ^b	
 • Avoid concomitant use and consider alternative with less CYP3A inhibitory potential. • If these inhibitors will be used short-term (such as anti-infectives for seven days or less), interrupt ibrutinib. • If the benefit outweighs the risk, and long-term dosing with a CYP3A inhibitor is required (more than seven days), reduce ibrutinib dose to 140 mg once daily for the duration of the inhibitor use.

- Monitor for adverse reactions to ibrutinib and interrupt or modify dose as recommended (see Dosage and Administration).
- Posaconazole at higher doses (posaconazole suspension 200 mg three times daily or 400 mg twice daily, posaconazole IV injection 300 mg once daily, posaconazole delayed release tablets 300 mg once daily).

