6.2.3. Antiplatelet Agents and Anticoagulants

Warfarin or other vitamin K antagonists as well as supplements such as fish oil and vitamin E preparations should be avoided if possible. Use ibrutinib with caution in subjects requiring anticoagulants or medications that inhibit platelet function. Subjects with congenital bleeding diathesis have not been studied. Study drug should be held at least 3 to 7 days pre- and post-surgery depending upon the type of surgery and the risk of bleeding (see Section 6.4).

For subjects requiring the initiation of therapeutic anticoagulation therapy (eg, atrial fibrillation), consider the risks and benefits of continuing ibrutinib treatment. If therapeutic anticoagulation is clinically indicated, treatment with ibrutinib/placebo should be held and not be restarted until the subject is clinically stable and has no signs of bleeding. No dose reduction is required when study drug is restarted. Subjects should be observed closely for signs and symptoms of bleeding.

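### Protocol Table 5 and Section 6.2.3 give different restart instructions after Grade 3 atrial fibrillation with anticoagulation, and Table 5's capsule counts fit only subjects on 560 mg

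*Protocol*

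**What the plan says.** The daily dose in protocol Table 3 (Section 5.3.1.2) is "560 mg (4 x 140 mg capsules) or placebo". Section 5.3.1.4 sets the scope of the toxicity rules: "For an ibrutinib/placebo-related adverse reaction, the recommendations for dose modification of ibrutinib/placebo are provided in" Tables 4 and 5.

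Table 5 covers cardiac failure and cardiac arrhythmia. At a first Grade 3 arrhythmia, and likewise at a first Grade 2 cardiac failure, study drug is held and the site is told to "restart at 1 dose level lower (3 capsules [ie, 420 mg daily". The footnote to the arrhythmia row adds "Evaluate the benefit risk before resuming treatment" and gives no dose. A second Grade 3 arrhythmia leads to discontinuation.

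Section 1.2.4.2 refers arrhythmias that persist to Section 5.3.1.4. That section in turn cites Section 6.2.3 for anticoagulant or antiplatelet use in atrial fibrillation. Section 6.2.3 has study drug held when therapeutic anticoagulation is indicated, and then says "No dose reduction is required when study drug is restarted".

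Other sections place subjects below 560 mg:

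- Section 5.3.1.5, for Child-Pugh A at enrollment or later: "the recommended dose reduction for ibrutinib/placebo is to a level of 280 mg daily (two capsules". For Child-Pugh B arising on study it names 140 mg.
- Section 6.2.1, for moderate CYP3A inhibitors: "imatinib, verapamil, amiodarone, dronedarone) is indicated, reduce ibrutinib dose as per recommended dose modifications in the table below". The table gives 280 mg. It gives 140 mg for voriconazole, for lower-dose posaconazole, and for long-term use of other strong inhibitors.

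The only text on toxicity steps for subjects already reduced to 280 mg stands between Tables 4 and 5: "dose level is to be reduced by one capsule to 140 mg at the second occurrence of AEs as described above".

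**The concern.** Atrial fibrillation is the case in which a toxicity rule and an anticoagulation rule are most likely to be read together, and the protocol's own cross-references lead the reader from one to the other. If the two give different restart instructions with no order of precedence, two sites can treat the same event differently and both be following the protocol.

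Table 5 also ties its steps to capsule counts that assume a 560 mg start, although the protocol expects some subjects to be on less.

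At stake is a consistent dosing instruction after a cardiac toxicity, in a population aged 60 and over, for a class of events in which Section 1.2.4.2 reports fatal cases. The SAP is touched as well. Section 3.4 summarizes relative dose intensity, reductions due to adverse events, and adjustments for CYP inhibitors, and differing site readings would blur those summaries.

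**Working it through.** No statistical calculation is involved. The check sets the passages side by side and uses the stated capsule size.

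**1. Reproducing Table 5's figure.** One capsule is 140 mg. Three capsules are 3 × 140 = 420 mg. One level below the assigned dose is 560 − 140 = 420 mg. Words and figure agree for a subject on 560 mg. Taking a level as 140 mg follows from the sequence 560, 420, 280 in Table 4 and from that table's footnote.

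**2. Subject on 560 mg, first related Grade 3 atrial fibrillation, therapeutic anticoagulation started.**

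| | Table 5 | Section 6.2.3 |
|---|---|---|
| Trigger | Related Grade 3 arrhythmia | Start of therapeutic anticoagulation |
| Condition for restart | Toxicity resolved to Grade 1 or less, or to baseline | Clinical stability and absence of bleeding |
| Dose on restart | One level down, 420 mg | No reduction required; no figure stated (560 mg if none is made) |

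The difference is 560 − 420 = 140 mg, one capsule. Section 1.2.4.2 points to 5.3.1.4, and 5.3.1.4 points to 6.2.3. Neither says how the rules combine when both triggers are met.

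**3. Subjects not on 560 mg at a first Table 5 event.**

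| Dose at event | The words (one 140 mg level down) | The bracketed figure | Figure ÷ dose at event |
|---|---|---|---|
| 560 mg | 420 mg | 420 mg | 420/560 = 0.75 |
| 280 mg | 140 mg | 420 mg | 420/280 = 1.5 |
| 140 mg | 0 mg, no capsule level left | 420 mg | 420/140 = 3.0 |

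At 280 mg and at 140 mg the two halves of one table cell cannot both be followed.

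**4. Whether the sentence for subjects on 280 mg closes the gap.** It precedes Table 5, refers back to events already described, and acts at a second occurrence. Table 5 acts at the first occurrence and, for Grade 3 arrhythmia, discontinues at the second. The sentence therefore has no step to offer in that row. It also sits badly with Table 4: once a subject has gone to 140 mg at the second occurrence, the third-occurrence row names 280 mg (280/140 = 2), again beside words that mean a step down. Neither this sentence nor any table row addresses a subject already on 140 mg.

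**5. Arrhythmia with a CYP3A inhibitor.** Section 6.2.1 fixes a dose for as long as the inhibitor is used. It does not say how that dose combines with the Table 5 step.

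**The case against.** The strongest answer is that the sections have different triggers and can be read together. Section 6.2.3 is about bleeding risk, its restart condition concerns bleeding, and it states no dose. On that reading it means only that anticoagulation by itself calls for no reduction, which leaves Table 5's toxicity step untouched. Section 1.2.4.2 supports this by routing arrhythmia dosing to 5.3.1.4. For subjects below 560 mg, the words of Table 5 plainly mean a step down, and the bracket can be taken as illustrating the standard dose. The footnote requires a benefit-risk judgment, the rules are called recommendations, and deviations go to the Medical Monitor.

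Much of this is fair. The combined reading of 6.2.3 is reasonable, but the section does not state it, and Section 1.2.4.2 speaks only of arrhythmias that persist. Calling the bracket an illustration does not supply an instruction for a subject on 140 mg, for whom no lower capsule level exists. Consulting the Medical Monitor helps with single cases but does not remove the contradiction from the text.

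It also stands that sites are blinded and apply the same rules in both arms, and that no effect on the primary PFS analysis has been shown. Child-Pugh B or C and continuous strong-inhibitor use are excluded at entry, so 140 mg would arise mainly from changes during the study.

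**Conclusion.** The point holds in two parts.

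1. For a first related Grade 3 atrial fibrillation with newly started therapeutic anticoagulation, Table 5 and Section 6.2.3 point to different restart doses (one 140 mg capsule apart for a subject on 560 mg) and state different restart conditions. How they combine is not stated.
2. Table 5's bracketed doses match its words only from 560 mg. At 280 mg and 140 mg they contradict them, and the sentence between the tables does not resolve this.

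This rests on the event being study-drug related and on one dose level meaning one 140 mg capsule.

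Three stronger readings are not supported:

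- A reader might infer that every Grade 3 atrial fibrillation draws three rival restart doses, with 280 mg from Section 6.2.1 as the third. That section gives a co-medication dose, which Section 5.3.1.4 itself cross-references. It applies only while an inhibitor is used, and the documents do not say that the listed inhibitors would be given for the arrhythmia. With neither co-medication, a subject on 560 mg meets only the Table 5 instruction.
- A reader might infer that Table 5 orders a dose increase for subjects on 280 or 140 mg. It does not: the same cell calls for a lower level, so the defect is a contradiction.
- A reader might want a count of affected subjects. The documents give no rate of Grade 3 arrhythmia, and a count of arrhythmias would still overstate the number, because each conflict also needs anticoagulation, an inhibitor or an earlier reduction.

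**What to change.** Reconcile Tables 4 and 5, the text between them, and Sections 5.3.1.5, 6.2.1 and 6.2.3. Each of these situations should lead to one consistent instruction:

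- an arrhythmia with therapeutic anticoagulation;
- an arrhythmia with a CYP3A inhibitor;
- a toxicity in a subject who is not on 560 mg at the event, at each occurrence.

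Where two sections apply at once, the text should say how they combine. The clinical team decides the doses and which rule governs; none is proposed here.

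The cost is one protocol clarification or amendment and a letter to sites. It adds no visits, tests or subjects and leaves the statistical design unchanged.

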5.3.1.5. Ibrutinib/Placebo: Dose Modification for Hepatic Impaired Subjects

Ibrutinib is metabolized in the liver and therefore subjects with clinically significant hepatic impairment at the time of Screening (Child-Pugh class B or C) are excluded from study participation. For subjects who have at enrollment or develop mild liver impairment while on study (Child-Pugh class A), the recommended dose reduction for ibrutinib/placebo is to a level of 280 mg daily (two capsules). For subjects who develop moderate liver impairment while on study (Child-Pugh class B), the recommended dose reduction is to a level of 140 mg daily (one capsule). Subjects who develop severe hepatic impairment (Child-Pugh class C) must hold study drug until resolved to moderate impairment (Child-Pugh class B) or better. Monitor subjects for signs of toxicity and follow dose modification guidance as needed (refer to [Appendix F](#)).

5.3.2. Rituximab

Rituximab (Rituxan[®]) is indicated for the treatment of patients with relapsed or refractory, low-grade or follicular, CD20-positive, B-cell NHL as a single agent ([MabThera[®] SmPC 2023](#), [Rituxan[®] USPI 2021](#)). In addition, rituximab, as a single-agent is currently a recommended therapy for elderly or infirm patients with previously untreated FL per clinical guidelines ([NCCN 2020](#), [Dreyling 2014](#)).

All subjects in Arms A and B will receive rituximab and will follow the regional labeling information for rituximab premedication, dosing and toxicity management ([MabThera[®] SmPC 2023](#), [Rituxan[®] USPI 2021](#)).

5.3.2.1. Rituximab: Formulation/Package/Storage

Rituximab is a highly purified 1328-amino acid antibody with an approximate molecular weight of 145 kD. The chimeric mouse/human anti-CD20 antibody is a glycosylated IgG1 immunoglobulin containing murine light- and heavy-chain variable regions and human γ 1 heavy chain and κ light-chain constant regions. Rituximab is a sterile, clear, colorless, preservative-free liquid concentrate for IV administration. Rituximab is supplied at a concentration of 10 mg/mL in either 100 mg (10 mL) or 500 mg (50 mL) single-use vials. The product is formulated for IV administration in 9.0 mg/mL sodium chloride, 7.35 mg/mL sodium citrate dihydrate, 0.7 mg/mL polysorbate 80, and Sterile Water for Injection. The pH is adjusted to 6.5 ([MabThera[®] SmPC 2023](#), [Rituxan[®] USPI 2021](#)).

Rituximab vials should be stored refrigerated between 2°C to 8°C (36°F to 46°F). Vials should be protected from light. Do not freeze or shake.

For more information regarding stability and storage refer to the Pharmacy Manual and regional labeling information ([MabThera[®] SmPC 2023](#), [Rituxan[®] USPI 2021](#)).

5.3.2.2. Rituximab: Dose and Administration

The first dose of rituximab will be administered IV beginning on Cycle 1, Day 1 in the Induction portion (Cycle 1) of the Treatment Phase. Rituximab will continue to be administered at the clinical site weekly for a total of four consecutive weekly doses. Rituximab doses during induction may be adjusted within a 3-day window due to scheduling conflicts. A minimum of 5 days between doses of rituximab is required.

Maintenance administration of rituximab will begin on Cycle 3, Day 1 of the Treatment Phase (5 weeks \pm 3 days after the last induction treatment on Cycle 1, Day 22) and continue every 8 weeks for a total of 12 doses (Cycle 3, 5, 7, 9, 11, 13, 15, 17, 19, 21, 23, and 25 on Day 1). Rituximab doses during Cycle 3 may be adjusted within a 3-day window. For Cycle 5 and beyond, rituximab maintenance administration visits may be adjusted within a 7-day window due to scheduling conflicts.

Dosage calculations for rituximab will be based on the subject's body surface area (BSA) based on height and weight obtained at the Screening visit. Actual body weight will be used for dose calculations. If the height and weight were not recorded at Screening, they may be obtained on Cycle 1, Day 1 and used for the dose calculations. Dose modification for changes in a subject's weight are not required per protocol but may be performed per institutional standard.

Rituximab will be administered IV by clinic staff according to the regional prescribing information. Premedication consisting of an analgesic/antipyretic (e.g., acetaminophen or paracetamol) and an antihistamine (e.g., diphenhydramine) should always be administered before each infusion of rituximab as outlined in the regional product information

(MabThera[®] SmPC 2023, Rituxan[®] USPI 2021). Premedication will be given prior to each administration. Rituximab should not be mixed or diluted with other drugs.

In the event of an infusion reaction, institute medical management (e.g., glucocorticoids, epinephrine, bronchodilators, or oxygen), as appropriate. If hypersensitivity (non-IgE-mediated) or an infusion reaction develops, the infusion should be temporarily slowed or interrupted.

Depending on the severity of the infusion reaction and the required interventions, treatment with rituximab may be temporarily or permanently discontinued. See Section 5.3.2.5 for further instructions.

Some individual subjects may require close monitoring during the first and all subsequent infusions, e.g., subjects who have pre-existing cardiac or pulmonary conditions, prior clinically significant cardiopulmonary AEs or high numbers of circulating malignant cells ($\geq 25,000/\text{mm}^3$) with or without evidence of high tumor burden.

Unused rituximab must be disposed of according to the sites drug disposal policy and drug accountability records updated.

